## C. Sample Size, Statistical Methods, and Power Calculation

### C1. Analytic and statistical methods (including randomization)

**Randomization.** Thirty-six primary care practices from the rural Midwestern U.S. will be randomly allocated in equal proportions (1:1:1) to each of the three arms (FFS, PCMH, DM). Randomization will be stratified by institutional affiliation (KUMC, UNMC, Marshfield Clinic) within three cohorts.

**Missing data.** Based on our prior history using a similar retention plan in the rural setting, we expect to retain a minimum of 80% of participants (with a goal of 90%) at 24 months across all three treatment arms. We will document reasons for loss to follow-up. Participants who are removed from study for pregnancy, bariatric surgery, medical safety reasons, behavioral problems, or death will be excluded from analyses. All primary analyses will be conducted using intent-to-treat. We will evaluate the missing data pattern for differential loss to follow-up based upon treatment arm. All of the covariates (other than the outcomes) will be collected at baseline, and with our data quality controls we don't expect this data to be missing. In the absence of differential loss to follow-up, missing weight data will be treated as missing at random and addressed using maximum likelihood methods.

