### **Primary aims 1-3: weight loss at 24 months and leading up to 24 months**

Weight loss at 24 months will be compared between PCMH vs FFS and DM vs FFS, as well as DM vs PCMH. Hierarchical linear mixed models will be used to examine the group differences, accounting for the correlation between patients from the same clinic.

We will fit a hierarchical linear mixed model with longitudinal weight change at 6, 18, and 24 months study visits. This model will account for the correlation between patients in the same clinic as well as correlation of measures from the same patient. In secondary analysis, percent weight loss will also be compared across the three groups using the same approach. Clinical cutpoints of 5% and 10% will be compared across arms at 6 and 24 months using generalized linear mixed models. The analytical plans may be adapted to provide the best approach using the latest methodological advancements.

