### **Secondary aim 6: evaluate the reach and sustainability of the interventions with the RE-AIM framework (Reach, Adoption, Implementation, Maintenance)**

Adoption within KUMC-affiliated sites will be evaluated by comparing practice characteristics across participating and non-participating practices (that were contacted about the study) using two sample comparisons (chi square or t-tests). After aggregating to the practice level, patient-level factors for reach (e.g., participation rates) and implementation (e.g., session attendance, ratings of care) will be tested and compared across arms using separate analysis of variance (ANOVA) models. Maintenance of weight loss services at the practice-level will be reported as simple frequencies.

**Potential confounders:** For all statistical models, sensitivity analyses will be performed using the models above but also adjusting for potential confounders among the baseline variables identified as varying across arms based on their standardized differences.

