### **C3. Power calculation and sample size**

A total of 36 practices with 40 participants per practice will be enrolled in the study (1440 participants total). Twelve practices (480 participants total) will be enrolled in each arm (FFS, PCMH, DM). A net treatment effect of 2.75 kg is supported by the available literature and our previous work. Treatment effects for PCP counseling alone with varying levels of intervention intensity have ranged from 0.1 to 1.7 kg at 12 to 24 months follow-up with the majority falling below 1 kg. For this pragmatic trial conducted in underserved rural areas, we expect the FFS treatment effect to fall in the lower end of this range. Team-based care approaches with obesity counseling delivered by auxiliary staff (PCMH) have ranged from 2.9 to 5.1 kg at 24 mo. In an entirely remote disease management program, Appel et al. reported weight loss of 4.6 kg at 24 mo. Our remote group phone-based program currently being delivered outside the primary care setting has shown 10.2 kg loss at 18 mo in preliminary analyses. We expect this to be lower in a pragmatic primary care trial, however a net effect  $\geq 2.75$  kg is achievable. To determine sample size, we set the type I error at 0.025 (overall type I error rate of 0.05 for first two aims), intraclass correlation coefficient at 0.05, and 40 patients/clinic. With 36 clinics, the trial will have 80% power to detect a net treatment effect of 2.75 kg (SD = 8).

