#### E5. Timeline (Figure 3)

The original funding period for this study was 5 years, January 1, 2015 to December 31, 2019. A global contract modification fully executed in February 2018 extended the period of performance through April 30, 2020. The final timeline is included in Figure 3. All project milestones, as required by PCORI, will be completed within this time frame. The study will be implemented in three cohorts, with 12 primary care practices in each cohort (4 in each of the 3 arms). Patient recruitment will begin in January 2016 for cohort 1, June 2016 for cohort 2 and September 2016 for cohort 3. Practices in the PCMH and DM arms will enroll 40 patients over a 6 month time period. The FFS arm will enroll 40 patients over a 9 month period (indicated in the timeline below with dotted lines). Each patient in all arms will be followed for 2 years. Analysis and dissemination of the primary outcomes will happen in the final 6 months of the project period.

Figure 3. Study Timeline

	Year 1 - 2015				Year 2 - 2016				Year 3 - 2017				Year 4 - 2018				Year 5 - 2019				Year 6 - 2020	
	Q1	Q2	Q3	Q4	Q1	Q2	Q3	Q4	Q1	Q2	Q3	Q4	Q1	Q2	Q3	Q4	Q1	Q2	Q3	Q4	Q1	Q2
Cohort 1	Study Preparation IRB Approval Practice Recruitment DSMB Charter Obesity Trainings			Practice Training	Recruitment		Phase 1		Phase 2										Analysis and Dissemination			
Cohort 2					Practice Training	Recruitment		Phase 1		Phase 2												
Cohort 3						Practice Training	Recruitment		Phase 1		Phase 2											

Figure 4. Study Flow

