#### **15. Communication**

[figure not shown]
The study team includes investigators and staff from the three institutions (KUMC, UNMC, and Marshfield Clinic) and personnel from the 36 local primary care practices (20 practices through KUMC, 6 through UNMC, and 10 through Marshfield Clinic); See Organizational Chart. The PI will meet with her research staff at least weekly to oversee all aspects of the study. The PI will meet with all co-investigators at KUMC, UNMC, and Marshfield Clinic at least monthly via conference call or Skype to discuss project updates, questions and concerns, and progress with recruitment and retention for each clinic to ensure consistency in study implementation across the three institutions.

Communication between primary care clinics and the affiliated institution will occur primarily between the Practice Coordinator (central study personnel) and Practice Liaison (clinic study personnel). The KUMC study team includes a full-time Lead Practice Coordinator responsible for coordinating implementation of the study protocols across the primary care clinics. In addition to working closely with the other Practice Coordinators (staff from KUMC and one each at UNMC and Marshfield Clinic), she will serve as the primary contact for approximately 12 clinics affiliated with KUMC. The Lead Practice

Coordinator will manage delivery of all provider trainings and regulatory compliance across all 36 clinics and facilitate communication with practices related to the study activities they oversee.

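### The primary weight-change model omits the randomisation strata and baseline weight, which forgoes power if the strata predict weight change; it also names no degrees-of-freedom method, which acts in the opposite direction

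*Combined protocol and SAP*

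**What the plan says.** Section II.C1 (Randomization) has the 36 practices "randomly allocated in equal proportions (1:1:1) to each of the three arms (FFS, PCMH, DM" and adds: "Randomization will be stratified by institutional affiliation (KUMC, UNMC, Marshfield Clinic) within three cohorts". Section II.E5 plans "12 primary care practices in each cohort (4 in each of the 3 arms". Section II.I (Communication) lists "36 local primary care practices (20 practices through KUMC, 6 through UNMC, and 10 through Marshfield Clinic".

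For the primary aims, II.C1 describes a multilevel linear model for change in weight at months 6, 18 and 24: "This model will account for the correlation between patients in the same clinic as well as correlation of measures from the same patient". It mentions no term for institution, cohort or baseline weight, and no df or small-sample method. The Potential confounders paragraph at the end of II.C1 says that "sensitivity analyses will be performed using the models above but also adjusting for potential confounders among the baseline variables identified as varying across arms", with selection by standardised difference and no cut-off. The Missing data paragraph refers to covariates gathered at baseline but lists none. The primary-aims paragraph also allows the analysis to be changed as methods develop, again without naming strata or df.

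On error rates, II.C3 says: "we set the type I error at 0.025 (overall type I error rate of 0.05 for first two aims".

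**The concern.** Stratified randomisation removes most between-strata variance from the comparison of arms. A model without the strata leaves that variance in its error term, so it reports a standard error larger than the true one. Factors that the design balances well are the ones most affected, and a rule that adjusts only for observed imbalance tends to pass them over.

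What is at stake is precision. A trial with 12 practices per arm may forgo power that its design has already paid for.

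The missing df method is a second, separate gap. With only 36 clusters, a normal reference distribution makes the test liberal, while t with appropriate df holds its size. The plan leaves this choice open.

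**Working it through.** **Inputs.** From II.C3: 12 practices and 480 patients per arm, 40 per practice, ICC 0.05, SD 8, difference 2.75 kg, type I error 0.025 (taken as two-sided; the sidedness is not stated). From II.I: 20/6/10 practices by institution. From II.E5: 4 practices per arm in each cohort. From II.C1: "we expect to retain a minimum of 80% of participants" at 24 months, which gives 0.80 × 40 = 32 per practice. Assumed, because the documents do not give it: the share of between-clinic variance due to strata.

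**1. The plan's power.** Clinic variance is 0.05 × 64 = 3.2 and residual variance is 60.8. SE = √[2 × (3.2/12 + 60.8/480)] = 0.887. Power = Φ(2.75/0.887 − 2.2414) = 0.805, which reproduces the stated 80%. That figure uses a normal reference and no strata.

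**2. The df choice alone.** Three arms and 36 practices leave 33 cluster-level df. On noncentral t with 33 df, power is 0.770. If a normal critical value is used instead, the true size is 2 × P(t33 > 2.2414) = 0.032 against 0.025.

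**3. What the imbalance rule can select.** Cohort is 4/12 in every arm, so at 40 patients per practice its standardised difference is 0. The closest institutional split over arms is KUMC 7/7/6, UNMC 2/2/2, Marshfield 3/3/4. One pair of arms then differs on no institution. The other two pairs differ by 0.083/0.497 = 0.17 on KUMC and 0.083/0.453 = 0.18 on Marshfield. With no cut-off stated, inclusion of institution is open.

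**4. Omitting strata, closed form.** The variance of a practice mean is 3.2 + 60.8/40 = 4.72. If balanced strata carry a share f of the clinic variance, the reported SE divided by the true SE is √[4.72/(4.72 − 3.2f)]. This is 1.04 at f = 10% and 1.10 at f = 25%.

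**5. Omitting strata, simulation.** Practice means were simulated with 20,000 trials per row. The assumed cells by institution were 7/2/3, 7/2/3 and 6/2/4 over the three cohorts. Institution and cohort contributed equally, and total ICC was held at 0.05. The model without strata uses t on 33 df and main effects use t on 29 df.

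| Assumed share | Size, no strata, t | Size, no strata, normal | Power, no strata, t | Power, main effects, t | Difference (points) |
|---|---|---|---|---|---|
| 0% | 0.025 | 0.032 | 76.9% | 75.4% | −1.5 |
| 10% | 0.023 | 0.028 | 77.1% | 78.4% | +1.3 |
| 20% | 0.016 | 0.021 | 78.4% | 82.2% | +3.8 |
| 30% | 0.015 | 0.020 | 78.1% | 85.1% | +7.0 |

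The adjusted model has size 0.025–0.027. At a 30% share the model without strata reports an SE of 0.894 against a true 0.81. Break-even is at a share of about 5% (77.3% against 77.4%).

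**6. Sensitivity.**
- Strata effects drawn at random instead of held at the stated share: gains of about 1/2/4 points at 10/20/30%.
- Only institution matters: size 0.020/0.018/0.017 and gains of about 1/4/7 points.
- Effects specific to institution-by-cohort cells: main effects recover only about 0.4/1.3/2.7 points.
- 32 per practice: 72.9/73.4/74.6/74.4% without strata against 71.8/74.6/78.4/81.2% with main effects, at 0/10/20/30%.
- Baseline weight: residual variance 60.8 × (1 − r²) moves power on t from 77.0% to 77.2% (r = 0.1) or 78.4% (r = 0.3). Both correlations with change are assumed.

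**The case against.** The strongest reply is that the harm rests on a quantity found nowhere in the documents. If the strata explain little, adjustment gains nothing or costs a point or two. This stands, and it is why the size is given as a range with a break-even.

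A reader might infer that the omission pulls the trial below its planned power. The documents do not support that. The II.C3 calculation assumes no strata adjustment, and with total ICC fixed at 0.05, power without strata on t does not fall as the share rises (76.9% to 78.1%). The loss is relative to a better model. It would fall below the plan's calculation only if strata variance came on top of the 0.05.

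A reader might also infer that the primary test is invalid, or that the plan is conservative overall. Neither follows. Omitting strata keeps size at or below 0.025 on t. With a normal reference, the missing df correction outweighs the conservatism at low shares (size 0.032 at 0% and 0.028 at 10%) but not at 20–30%. The plan fixes neither the df method nor the share, so the net direction is undetermined.

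Three further objections stand in part. The institutional differences of 0.17 and 0.18 do not apply to every pair of arms. Main effects are simpler than the nine cells within which practices are randomised. The plan mentions baseline covariates and allows adaptation, so it does not exclude strata; but a general allowance does not prespecify a model.

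**Conclusion.** The concern holds as a mismatch between randomisation and analysis that costs efficiency. The primary model names neither stratification factor nor baseline weight, and the imbalance-driven sensitivity analysis does not fill the gap. If the strata explain more than about 5% of between-clinic variance, the reported standard errors are too large. At shares of 20–30% the t test has size of about 0.015–0.02 and about 2–7 power points are forgone relative to a strata-adjusted model, depending on how the share is defined. These figures rest on the assumed share, the assumed spread of institutions over cohorts and equal practice sizes.

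The unstated df method is a separate gap that acts the other way, with size of about 0.032 under a normal reference when the strata explain nothing. The two should be settled together, because fixing one alone changes the balance between them.

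**What to change.** In II.C1, under the primary aims, prespecify weight change by arm × visit with fixed main effects for institution and cohort, baseline weight as a covariate, and a small-sample df method such as Kenward-Roger. Report the model without strata and baseline weight, using the same df method, as a sensitivity analysis. Keep the imbalance-driven adjustment as supplementary.

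Main effects are preferable to nine cells. UNMC has 6 practices over three cohorts. In a separate run of 8,000 trials with strata explaining nothing, power was 76.1% without strata, 74.9% with main effects and 71.9% with nine cells.

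No new data are needed: institution and cohort are known for every practice, and II.E2e already has weight measured at baseline. The cost is four cluster-level df (33 to 29) and about 1–2 power points if the strata explain nothing. Main effects also recover only part of the loss if effects are specific to institution-by-cohort cells.

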## **C2. Blinding**

Randomization happens at the practice level. Blinding practice staff or study staff is not feasible during a behavioral trial. However, throughout the study investigators and study personnel will communicate and

demonstrate equipoise (genuine uncertainty) with practice staff and patients about the relative benefit of the three arms.

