### **D3. Withdrawal/termination criteria**

#### *Medical Removal for Safety Purposes*

Participants who experience an injury or new medical condition for which exercise or weight loss may be contraindicated will be asked to see their medical provider for treatment and evaluation. After consultation with the KUMC study physician and/or the practice study PCP, participants will be removed from the study if the onset of a medical condition contraindicates their participation. Participants will be removed for pregnancy past the first trimester and bariatric surgery while on study.

Members of the study team, the care coordinators/counselors, and the PCPs retain the right to remove a participant from the study if it is deemed that the participant is unsuitable for group or individual weight loss counseling sessions due to behavioral problems caused by mental illnesses, substance abuse, or any other reason.

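### The plan leaves participants removed on study out of the analyses yet calls the primary analysis intent-to-treat; the stated set is a modified one and should be redefined

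*Combined protocol and SAP*

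**What the plan says.** The missing-data paragraph of II.C1 has two adjacent sentences: "Participants who are removed from study for pregnancy, bariatric surgery, medical safety reasons, behavioral problems, or death will be excluded from analyses" and "All primary analyses will be conducted using intent-to-treat". The same paragraph says that reasons for loss will be documented, that "We will evaluate the missing data pattern for differential loss to follow-up based upon treatment arm", and that "In the absence of differential loss to follow-up, missing weight data will be treated as missing at random and addressed using maximum likelihood methods".

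For the primary aims, II.C1 says "We will fit a hierarchical linear mixed model with longitudinal weight change at 6, 18, and 24 months study visits". A likelihood-based model of this kind can use participants who have some but not all of these weights.

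Removal is described in II.D3. "Participants will be removed for pregnancy past the first trimester and bariatric surgery while on study". Study team members, counselors and PCPs may also remove anyone they consider "unsuitable for group or individual weight loss counseling sessions due to behavioral problems caused by mental illnesses, substance abuse, or any other reason". II.K3 leaves medical removal to the treating PCP in communication with the PI and study physician. On masking, II.C2 says "Blinding practice staff or study staff is not feasible during a behavioral trial".

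No section defines a modified intent-to-treat set, limits the exclusion to weights after the removal event, or plans an analysis that puts removed participants back.

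**The concern.** Intent-to-treat normally means that everyone who entered the trial is analysed in the arm to which they were allocated, whatever happened afterwards. Practices are randomised, and II.I4 says that the consent form differs by arm, so the arm is fixed before a participant enrols. Every on-study removal is therefore a post-allocation event, and dropping people for it conditions the comparison on something the arm may influence.

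That influence is plausible here. Pregnancy, bariatric surgery and death are largely matters of fact. Medical and behavioral removals are judgements made by people who know the arm. The behavioral criterion is open-ended and refers to suitability for group or individual sessions, which is part of what separates the arms. II.K3 also mentions possible removal for unresolved exercise injuries in the text on the DM arm. For FFS and PCMH it says only that non-serious exercise events stay under the PCP's control.

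At stake is who enters the 24-month contrast. If removal rates or removed participants' outcomes differ by arm, the contrast is biased. A reader told that the analysis was intent-to-treat would have no reason to look for this. Two analysts could also build different primary datasets from the same paragraph.

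**Working it through.** **1. The text.** The object excluded in the first sentence is participants, not visits. On its plain wording the set is all enrolled participants minus those removed for the five reasons. Reading intent-to-treat as *regardless of session attendance* (III.C4 expects attendance to differ by arm) does not reconcile the sentences, because removal is not non-attendance. The check for differential loss does not help either: it describes the pattern but does not restore anyone.

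**2. The plan's own power figure.** Inputs from II.C3: 12 practices per arm, 40 per practice, SD 8 kg, ICC 0.05, effect 2.75 kg, type I error 0.025. Sidedness is not stated; two-sided reproduces the figure.
- Design effect = 1 + (40 − 1) × 0.05 = 2.95.
- SE of the contrast = √(2 × 64 × 2.95 / 480) = 0.887 kg.
- Power (normal) = Φ(2.75/0.887 − 2.241) = 80.5%, against the stated 80%.

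**3. Precision lost by excluding people.** With m participants per practice, SE = √(2 × 64 × (1 + (m − 1) × 0.05) / (12m)).

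| Removed (assumed) | m | SE, kg | Power |
|---|---|---|---|
| 0% | 40 | 0.887 | 80.5% |
| 4% | 38.4 | 0.893 | 79.9% |
| 10% | 36 | 0.903 | 79.0% |

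The loss is negligible.

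**4. Possible shift in the contrast.** Let p be the share removed in an arm and d the mean 24-month weight loss of kept minus removed participants. The all-enrolled mean is (1 − p) × kept + p × removed, so excluding the removed overstates that arm's loss by p × d. The contrast shifts by p₁d₁ − p₀d₀, where 1 is the active arm and 0 is FFS. The documents give neither p nor d; the values below are assumptions. They illustrate medical and behavioral removals only, because a 24-month gap is not a sensible quantity after death and means something different after surgery or pregnancy.

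- Equal rates and equal gaps: 0 kg.
- 4% vs 2%, gap 5 kg in both arms: 0.04 × 5 − 0.02 × 5 = 0.10 kg (4% of 2.75).
- 4% vs 2%, gap 10 kg in both arms: 0.04 × 10 − 0.02 × 10 = 0.20 kg (7% of 2.75).
- 2% in both arms, gaps 10 and 5 kg: 0.02 × 10 − 0.02 × 5 = 0.10 kg.
- Rates of 1, 2 or 4% per arm with a common gap of 5 or 10 kg: −0.30 to +0.30 kg. The range reaches ±0.40 kg only if one arm has a 10 kg gap and the other none.

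At a true difference of zero, shifts of 0.10 and 0.20 kg move the two-sided error from 0.025 to 0.026 and 0.029.

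**5. What it would take to matter more.** A shift of 10% of the design effect is 0.275 kg. At a 5 kg gap this needs a removal difference of 0.275/5 = 5.5 points (26 of 480); at 10 kg, 2.75 points (13 of 480).

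**6. What keeping earlier weights would recover.** Suppose removal happens after month 6 and depends only on month-6 change, with month-6 gap g (the same in both arms) and slope b of month-24 on month-6 change. Exclusion shifts the contrast by (p₁ − p₀) × g × b. With 4% vs 2%, g = 4 to 6 kg and b = 0.6 to 0.8, all assumed, that is 0.02 × 4 × 0.6 = 0.05 kg to 0.02 × 6 × 0.8 = 0.10 kg. Under this mechanism a correctly specified maximum-likelihood model that keeps the month-6 weights has no such bias.

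**The case against.** The strongest reply is that the exclusion is open and prespecified by reason, and that its likely effect is small. II.D2 already excludes planned bariatric surgery, planned pregnancy and several recent serious illnesses, and it gives the avoidance of major confounding of the endpoint as part of its purpose. That removes some foreseeable cases and gives a rationale for setting aside weights after surgery or pregnancy. The 5 to 10 kg gaps may also be high: under the mechanism in step 6, the implied 24-month gap is only 4 × 0.6 = 2.4 kg to 6 × 0.8 = 4.8 kg. All of this stands, and it limits the severity. It does not make the set intent-to-treat, and screening at entry does not say how removals that still occur are analysed.

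Two stronger readings are tempting. A reader might infer that the plan definitely discards the earlier weights of removed participants. That is the plain wording, but the sentence sits in a paragraph on missing 24-month data, and the authors may have meant only to stop using weights after the event. The documents leave it unclear. A reader might also infer that the primary result will be materially biased, or biased towards the group arms. Without removal rates or outcomes the documents support neither a size nor a direction.

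**Conclusion.** The point holds as a defect in the definition of the primary analysis set: the plan describes a modified intent-to-treat set, calls it intent-to-treat, and does not say what happens to weights measured before removal. It is wrong as written and should be fixed. It is not evidence that the trial's conclusion would change.

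The textual conclusion needs no assumption beyond the usual meaning of intent-to-treat. The size rests entirely on assumed rates and gaps: 0.1 to 0.2 kg for 2% vs 4% removal with a 5 to 10 kg gap, zero if rates and gaps are equal, and either sign possible. These figures are illustrations, not bounds; 5% vs 10% at a 10 kg gap would give 0.10 × 10 − 0.05 × 10 = 0.5 kg. The issue is possible bias and a misleading label, not power.

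**What to change.** Replace the exclusion sentence in II.C1 with wording to this effect:

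- The primary analysis includes every enrolled participant under the practice's allocated arm, and all weights measured before removal stay in the maximum-likelihood mixed model.
- Weights after pregnancy or bariatric surgery are not used, and none exist after death. State this as an explicit estimand choice, since setting aside observed weights departs from strict intent-to-treat.
- After medical or behavioral removal, later weights are used where available and where consent permits, including through the chart review that II.E2e and III.C4 already allow. Otherwise they are treated as missing.
- Removals are tabulated by arm and reason, extending the documentation of losses already planned.
- The present exclusion set is reported as a sensitivity analysis labelled modified intent-to-treat.

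The plan states maximum likelihood only for the case of no differential loss, so the new wording should say that the method applies to removed participants' missing weights.

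The cost is a few sentences, one extended table and one extra model run, with no added visits or patients. Using weights after removal may need consent wording; the consent forms are not in this copy, so that cannot be judged here. Some bias can remain if removal depends on later weight that is never observed. No clinical removal rule changes.

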### K3. Patient safety

If central study personnel become aware of new or worsening medical symptoms through information reported by patients during retention phone calls or during counseling sessions in the DM arm, they will refer the patient back to their PCP. Study laboratory results will be sent directly to the PCP per their standard operating procedures. Panic or critical value laboratory results will be managed per their standard operating procedures as well. All providers will be trained in SAE reporting during the central training and in ongoing discussions with the practice throughout the course of the study. Overall management of diabetes, hypertension, cardiovascular disease, and other medical conditions remains under the control of the treating PCP. The treating PCP, in communication with the KUMC PI and study physician, will determine if it is unsafe for the participant to remain in the study based on a change in medical status.

***Exercise-related AEs.*** If a cardiovascular event occurs during prescribed exercise, the physical activity component of the intervention may be suspended and/or later resumed with possible modifications after approval from the treating PCP. For exercise-related events and injuries for patients in the DM arm, the study clinician and/or the treating PCP will be consulted according to the symptoms reported. If appropriate, the participant’s exercise goals or type will be modified. If the symptoms or injury do not resolve after an appropriate period of time, the participant will be referred to his or her PCP for further evaluation and may

be removed from the study. In the FFS and PCMH arms, management of any non-serious exercise-related AEs remains under the control of the PCP.

*Diet-related AEs.* If participants suffer negative health consequences from consuming nutritionally inappropriate diets (such as rapid weight loss, gallstones) and counseling to change nutritional intake have been ineffective, the treating PCP (in consultation with the central counselors for the DM arm) may decide to suspend the intervention. This scenario is uncommon but may occur.

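### Participants removed for medical safety reasons are excluded from analyses that the plan calls intent-to-treat

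*Combined protocol and SAP*

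**What the plan says.** Two consecutive sentences in II.C1 (Missing data) set the rule: "Participants who are removed from study for pregnancy, bariatric surgery, medical safety reasons, behavioral problems, or death will be excluded from analyses", and then "All primary analyses will be conducted using intent-to-treat". The plan defines no modified analysis set and gives no estimand rationale for the exclusion.

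II.D3, under the heading "Medical Removal for Safety Purposes", starts from "Participants who experience an injury or new medical condition for which exercise or weight loss may be contraindicated". These participants are sent for evaluation. After consultation with a physician, "participants will be removed from the study if the onset of a medical condition contraindicates their participation". II.K3 adds that the treating PCP, in communication with the PI and the study physician, "will determine if it is unsafe for the participant to remain in the study based on a change in medical status". II.C2 says that neither practice staff nor study staff can be blinded.

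For the primary aims, "We will fit a hierarchical linear mixed model with longitudinal weight change at 6, 18, and 24 months study visits". The only sensitivity analyses described, at the end of II.C1, are of one kind: "sensitivity analyses will be performed using the models above but also adjusting for potential confounders".

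**The concern.** A participant enrolled in a randomised practice and later taken out for a medical reason belongs in an intent-to-treat analysis. The plan removes that person from the analysis altogether. The decision is made after randomisation, by people who know the arm, on an event that may be related to treatment.

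If removed participants lose less weight than the others, leaving them out overstates an arm's mean loss. If removals, or the gap in weight loss, differ between arms, the contrast with FFS is biased. A removed participant whose illness itself causes weight loss pushes the other way, so the sign is not fixed in advance.

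The loss may also be permanent. If removal ends the assessment visits, no later sensitivity analysis can recover weights that were never taken.

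**Working it through.** **Does anything in the plan bring these participants back?** Four places might.

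- *Maximum likelihood under missing at random (II.C1).* It applies to missing weights. These participants are excluded, not treated as missing.
- *Home visits and chart weights (II.E2e, III.C4).* They serve patients who cannot come in or who miss a visit. Removed participants are not mentioned, and a weight so obtained would still be excluded.
- *Two-year follow-up of each patient (II.E5).* This is a timeline statement that does not address removal.
- *Sensitivity analyses (end of II.C1).* They add covariates and do not change who is analysed.

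None does so. The primary model uses weights at 6, 18 and 24 months, so a literal reading also drops values observed before removal.

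**Design standard error.** Inputs from II.C3: 12 practices and 480 participants per arm, 40 per practice, ICC 0.05, SD 8 kg, target 2.75 kg, type I error 0.025 per comparison.

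- Design effect: 1 + 39 × 0.05 = 2.95
- Effective n per arm: 480 / 2.95 = 162.7
- SE of a contrast: sqrt(2 × 64 / 162.7) = 0.887 kg
- Power, two-sided normal formula: Φ(2.75/0.887 − 2.241) = 80.5%, which reproduces the stated 80%

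**Shift from the exclusion.** Let p be the share of an arm removed, and d the 24-month loss in the rest of the arm minus that in removed participants. The full-arm mean loss is (rest − p·d), so exclusion overstates it by p·d. The contrast shifts by the difference of p·d between the two arms. The values of p and d are assumptions. One to three percent of 480 is about 5 to 14 people. A 5 kg gap means almost no loss among those removed, given the 24-month losses of 2.9-5.1 kg cited in II.C3.

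| Removal, one arm v the other | d = 1 kg | d = 3 kg | d = 5 kg |
|---|---|---|---|
| 1% v 0 | 0.01 | 0.03 | 0.05 |
| 3% v 0 | 0.03 | 0.09 | 0.15 |
| 2% v 1% | 0.01 | 0.03 | 0.05 |
| 3% v 1% | 0.02 | 0.06 | 0.10 |
| equal rates and gaps | 0 | 0 | 0 |

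If removed participants lose 3 kg more than the rest, 3% v 0 gives 0.03 × (−3) = −0.09 kg.

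**Size of the largest value, 0.15 kg.** It is 0.15/2.75 = 5.5% of the target and 0.15/0.887 = 0.17 of the SE. The two-sided type I error becomes Φ(−2.241 + 0.169) + Φ(−2.241 − 0.169) = 0.027 instead of 0.025. The shift is linear in both inputs: 10% v 2% with an 8 kg gap would give 0.08 × 8 = 0.64 kg, but nothing in the documents suggests such rates for medical removals.

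**Would keeping only earlier weights be enough?** Suppose the 6-month weight stays in the likelihood and nothing is measured after removal. With equal SDs, 6-to-24-month correlation ρ (assumed 0.5-0.8) and a 6-month gap d6, the remaining shift is p(d − ρ·d6). With p = 3% and d = d6 = 5 kg it is 0.15 × (1 − ρ), or 0.075 kg at ρ = 0.5 and 0.03 kg at ρ = 0.8. If the gap arises only after 6 months (d6 = 0), all 0.15 kg remains. Weights after removal are therefore needed too.

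**The case against.** The strongest case against has four parts.

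*Injury rarely means removal.* A reader might infer that every injured participant is dropped. The documents do not say so. In II.D3 an injury leads to evaluation, and removal requires a contraindicating condition. The injury-specific removal in II.K3 is discretionary and written for the DM arm. II.F1 defaults to modifying the exercise and, if symptoms persist, a PCP visit. This stands, and it narrows the point to those actually removed.

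*No arm difference is shown.* A reader might also take the 3% excess of musculoskeletal injuries cited in II.F1 as evidence that removals will differ by arm. That excess is lifestyle intervention against placebo. Here exercise is part of all three arms (II.F1), the activity recommendations are the same in each (II.E2a), and FFS has the same 225 min/week target (II.E2c). The figure says nothing about PCMH or DM against FFS. This also stands.

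*The effect is small and its inputs are assumed.* Correct. The removal rates and gaps have no source in the documents.

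*It is a prespecified population choice.* The rule is stated in advance and worded alike for all arms, and II.D2 excludes comparable conditions at entry. But an entry criterion acts before enrolment; this rule acts on follow-up events, through unblinded judgement. The plan presents the result as intent-to-treat, not as a different estimand. This part does not answer the contradiction.

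**Conclusion.** The point holds in a limited form. Followed as written, the plan leaves participants removed for medical safety reasons out of its primary analysis, and that analysis is not intent-to-treat. The contradiction rests on the text alone and needs no assumption.

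The likely numerical effect is small: 0.01-0.15 kg if removals of 1-3% occur in one arm only with a gap of 1-5 kg, and zero if rates and gaps match. Direction is unknown. The documents do not support saying that the rule favours any arm, or that it threatens the conclusion of the trial. The cost in power is also slight: by the same formula, 79.0% with 90% retained and 78.6% if a further 2% are excluded.

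The other four reasons in the same sentence (pregnancy, bariatric surgery, behavioral problems, death) are not assessed here. Some may be defensible as an estimand choice.

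**What to change.** 1. In II.C1, state that participants removed for medical safety reasons stay in the primary intent-to-treat model with all available weights, before and after removal. Use their exclusion only as a sensitivity analysis. Tabulate removals by arm and reason, alongside the loss-to-follow-up reasons and the arm check already promised there.
2. In II.D3 and II.K3, separate stopping or modifying the intervention from leaving assessment. The 6-, 18- and 24-month weights, taken in clinic, at home or from the chart, continue unless the participant withdraws consent.

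The cost is wording in three sections. The weights are already scheduled for every participant, and home visits and chart review are already allowed. The downsides are a slight dilution of the estimate and that some removed participants may decline further visits. If visits have already ended, weights measured before removal and any chart weights can still be included.
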